## Main Study

[figure not shown]
For power settings at 90W (Figures 6.3.1C and 6.3.1D), the maximum duration is set to 4 seconds. Therefore, the approach is to only titrate power. At this setting, power delivery is delivered at a constant irrigation flow of 8 ml/min with no modulation given the short duration.

[figure not shown]
## Figure 6.3.1A-D: Graphs of the Generator Power over Time

[figure not shown]

C. RF Power Delivery at 90W

D. RF Power Delivery at 90W, power titration evident

#### Second (Variable Flow) Study

RF energy modulation for Variable Flow rate:

The QDOT MICRO catheter is designed to work in a temperature control/power and irrigation modulation mode. This is how the system works for QMODE (refer to Figures 6.3.1A and Figure 6.3.1B above). However, when making 90W RF applications with a constant irrigation flow (8 mL/min) the system only worked in power control mode.

The purpose of the variable flow irrigation option is to improve the catheter tip temperature response during high power, short duration (Qmode+) ablations. This is

[figure not shown]
	Biosense Webster, Inc	
Version 5.0 – Feb 3, 2021	CONFIDENTIAL	

achieved by optimizing the flow rate (4-15 mL/min), which minimizes the impact of constant irrigation (8 mL/min) on the lack of catheter tip temperature response during short duration (4s) 90W RF applications (refer to Figure 6.3.2A and Figure 6.3.2B).

[figure not shown]
For power settings at 90W (Figures 6.3.2A and 6.3.2B), the maximum duration is set to 4 seconds. Therefore, the approach is to only titrate power. At this setting, power delivery is delivered with a variable flow rate. Irrigation at 4 mL/min starts with the initiation of 90W energy application. The flow rate remains at 4 mL/min if the catheter tip temperature remains below the target energy cutoff temperature (refer to Figure 6.3.2A). If the catheter tip reaches the target temperature, irrigation is then changed to 15 ml/min automatically by the generator algorithm. This increase in irrigation flow rate cools the tip and allows the generator to maintain the delivered power (refer to Figure 6.3.2B).

## Figure 6.3.2A-B: Graphs of the Generator Power over Time

A. Example 1 at 90W: Temperature does not approach Target Temperature (flow rate 4mL/min)

B. Example 2 at 90W: Temperature approaches Target Temperature (flow rate changes to 15 mL/min)

## 6.4 Potential Risk and Benefit

After over two decades of intracardiac radiofrequency (RF) catheter ablation, the procedural risks and complications associated with routine RF ablation are well documented and understood. Procedural risks posed by the QDOT MICROTM catheter are expected to be comparable to these known anticipated risks.[3, 4, 20]. Few, if any, additional risks that might occur during and following RF ablation of symptomatic PAF are anticipated for subjects enrolled in this study.

A summary of risks associated with catheter ablation, including analysis of and plans to minimize these risks is provided below:

#### 6.4.1 Description and Analysis of Risks

#### Risks associated with catheter ablation

Studies have reported low rates of major complications (0.8%)[21, 22] with major centers worldwide reporting rates lower that <5%[23, 24] associated with catheter ablation. The most common complications associated with catheter ablation of AF include:

**Cardiac tamponade** is reported at approximately 0.2 to 5% in catheter ablation of atrial fibrillation (AF)[4], comprising mainly pulmonary vein isolation (PVI) procedures. Data presented by recent meta-analysis of 34,943 ablation procedures by Michowitz et al reported incidence of 0.8%[25]. Rates as low as 0.18% have also been reported in a recent study that reviewed complications among 2,750 procedures[22].

The general incidence of pericardial effusion during AF ablation is around 1.2% to 1.3%[21, 23]. Cardiac perforation may result from catheter manipulation or application of radiofrequency current. Published risks of cardiac perforation range from <1%to 2.4%[23]. However the risk of perforation is decreased with advances in catheter technology[26]. This potentially life-threatening injury may result in cardiac tamponade and may require percutaneous pericardial drainage or surgical repair. Significant hemodynamic compromise can result in neurologic injury or death. An increased risk of cardiac perforation may be associated with the use of a saline-irrigated electrode catheter due to its ability to create a larger, deeper RF lesion. This risk is greatest in a thin walled chamber (i.e., RA, LA, appendage, or RV).

**Pulmonary vein stenosis**: Pulmonary vein stenosis (PVS) is a well-known complication of radiofrequency catheter ablation of atrial fibrillation. Incidence of severe PVS (>70% diameter reduction) was found to be <1% in a recent study with 976 subjects[27]. Incidence of only 0.5% was reported in a large systematic review on complications of radiofrequency catheter ablation.

**Esophageal injury**: Since the left atrium has close anatomical proximity to the esophagus, catheter ablation on the LA posterior wall may thermally damage the esophagus and eventually generate an esophageal ulcer with a prevalence of 5% [28] that rarely may progresses to an atrial esophageal fistula (AEF) with catastrophic consequences[29]. Esophageal injury by endoscopy has a prevalence between 2.2 to 21%[28]. Esophageal perforation is a dreaded complication of atrial fibrillation ablation that occurs in 0.02 to

Biosense Webster, Inc b 3, 2021 CONFIDENTIAL 11% [28, 30] of atrial fibrillation ablation procedures. Delayed diagnosis is associated with the development of atrial-esophageal fistula (AEF) and increased mortality. Complication rates for esophageal injury are quite varied, depending upon lesion location and type of lesion found (erythema, necrotic ulceration, perforation, or fistula formation). The incidence of AEF post-ablation of AF is supposed to be around 0.1% of the procedures[31]. Studies using luminal temperature monitoring to identify potentially dangerous heating of the esophagus during ablation have not been able to demonstrate reduction in incidence[32].

**Phrenic nerve paralysis**: Currently, this complication has been reported in less than 0.5%, with permanent paralysis between 0% to 0.4% when the isolation of right PV is not obtained during PV antra isolation and RF ablation is performed inside at carina the right PVs [4, 32, 33]. A 2018 published study reported very low rates of PNP of 0.04% among 2,750 procedures[22]. Prior to ablation in the region of the RSPV, investigators are encouraged to perform precautionary measures such as evaluation of proximity to the phrenic nerve and pacing maneuvers.

**Death** is an uncommon complication associated with CA techniques. Overall incidence of death has been reported to be <0.1% to 0.4%[4]. A 2010-published global survey provided an overall mortality rate of 0.1%. Another report from an international survey of AF ablation of 162 centers provided details on 32 deaths that occurred during or after AF ablation procedures in 32,569 patients (0.1%)[34, 35]. Among the most frequent causes of death were cardiac tamponade (25% of deaths), stroke (16%), atrio-esophageal fistula (16%) and massive pneumonia (6%)[35].

Radiofrequency current may cause occlusion of a coronary artery, either by direct thermal damage, spasm, or thrombus formation. Acute coronary artery occlusion is a very rare but potentially life-threatening complication of RFCA[36]. Experience at numerous centers suggests that the risk of coronary occlusion is less than 0.5%[37]. Coronary arterial occlusion could produce myocardial infarction (MI), angina or death. Occlusion of a coronary artery can be treated by restoring coronary blood flow through pharmacological, catheter and/or surgical intervention as medically indicated.

The application of radiofrequency current close to the AV node or His bundle could damage or destroy the normal AV conduction system, producing complete heart block and requiring implantation of a permanent pacemaker.

**Thromboembolic events:** Thrombus generation during the procedure may pose a serious and even life-threatening risk to the patient. Thrombus may form on the ablation electrode during the application of radiofrequency current with or without any change in impedance. The thrombus might become dislodged and embolize to produce an ischemic stroke, MI, or other occlusive injury. Although some observational studies have shown a relatively lower stroke rate after catheter ablation, whether catheter ablation can reduce the thromboembolic risk remains unclear.

The mean incidence of thromboembolism associated with AF ablation was reported by Cappato et al in 2010 to be between 1% and 2%[23]. More recently, Fuji et al have reported

Biosense Webster, Inc CONFIDENTIAL incidence of thromboembolism up to 5% of patients undergoing AF ablation despite perioperative anticoagulation[38]. Ischemic stroke events typically occur within 24 hours of the AF ablation procedure with the higher risk period covering for the first two weeks following ablation[39].

Pulmonary hemorrhage is a rare but severe complication of PVI. Late hemoptysis and pulmonary hypertension can occur secondary to pulmonary vein stenosis (PVS) after ablation. Acute pulmonary hemorrhage also has been reported[40]. Mechanical trauma from catheter manipulation is a possible mechanism for pulmonary hemorrhage[41]. Injury to a cardiac valve may result from catheter manipulation or the application of radiofrequency current (risk <1%)[42]. This may produce valvular insufficiency and possibly require valve replacement surgery.

**Vascular access** / **bleeding complication**: Arterial or venous injury, including arterial dissection, thrombosis, occlusion or hemorrhage at the catheter insertion sites or at other sites along the vessels (risk 0.2% to 1.5%).[4, 43, 44] These types of injuries may cause hemorrhage, hematoma or ischemic injury to an extremity or major organ.

Hemorrhage could occur as a result of anticoagulation (risk < 0.5%), which may require transfusion.[43, 44]

**Radiation exposure**: Radiation exposure during the fluoroscopic imaging of the catheters may result in an increase in the lifetime risk of developing a fatal malignancy (0.1%) or a genetic defect in offspring (0.002%).[45-47]

Allergic Reaction: A patient could develop an allergic reaction to the local anesthetic, sedatives, x-ray dye, heparin, protamine, or other agents administered during the procedure (risk < 1%).[48-52]

**Infection**: The percutaneous procedure carries risk of infection, either at the catheter insertion site or systemically, including endocarditis and septic emboli (risk < 0.5%).[43, 44] This risk can be minimized by using standard aseptic technique and, when indicated, by the use of antibiotic agents.

Additional contraindications: Additional contraindications for RF ablation include: hemodynamic instability, bacteremia, coagulopathy, prosthetic tricuspid valve, intra-atrial or venous thrombosis, and pregnancy.

### Investigational device related risks

A review of the testing of the investigational devices verifies that risks associated with the designs are acceptable and no unacceptable (Intolerable) risks have been noted. Any testing deviations are discussed within the body of the respective testing reports and all deviations were reviewed and considered to be acceptable.

The designs of the investigational devices have been subjected to testing (bench top, thigh preparation, simulated clinical conditions via in vivo beating heart testing and

Biosense Webster, IncVersion 5.0 – Feb 3, 2021CONFIDENTIAL

EMC/Electrical Safety testing). The results of the various testing performed have verified the safety of the investigational devices when used in accordance with the Instructions for Use.

Biocompatibility and Sterility Assessments for the applicable investigational devices have been performed and verify that the proposed design and packaging meet the existing requirements for both categories.

A review of the risk assessment documents for the investigational devices has verified that there are no "Intolerable" ratings related to risks associated with the designs of the devices. All ratings are "As Low As Practical" (ALAP).

### 6.4.2 Minimization of Risks

Appropriate measures have been outlined in the study protocol to minimize the risk to subjects, while still providing the possible benefits of the treatment options to be studied. Although there are potential risks posed during a cardiac RF ablation procedure, the criteria for subject selection, methods, personnel, facilities, and training that have been specified for this study are intended to minimize the risk to subjects undergoing this procedure.

Robust testing of the investigational devices at component and the system level, within simulated clinical conditions, was successful with no adverse events identified. During the QMODE+ design phase, systematic proactive risk analyses did not identify new hazards and harms. Additionally, the risk of potential adverse events is mitigated by the temp cutoff setting of the generator and the optimization of the target temperature.

Subjects will be screened carefully prior to enrollment in the study to ensure compliance with the inclusion and exclusion criteria. The exclusion criteria have been developed to eliminate confounding co-morbidities that might interfere with study interpretation; to furnish a more homogenous study population that allows a focused characterization of the QDOT MICRO™ catheter for the treatment of PAF; exclude subjects with a medical history or condition that increases their risk of adverse events. Subjects will be evaluated for presence of left atrial thrombus prior to the procedure. Additionally, using esophageal monitoring techniques will be used while ablating the posterior wall, thus minimizing risk of injury.

Participating investigators will be experienced and highly skilled in performing electrophysiology studies, intracardiac mapping and ablation of AF with the use of RF ablation catheters. Each site's Principal Investigator will have satisfied the established training criteria. Procedures will be performed in electrophysiology laboratories with the assistance of skilled nurses and technicians. The laboratory will contain sufficient resuscitative equipment and facilities to manage any potential complication. Immediate access to cardiac surgical facilities, as well as a qualified cardiovascular surgeon, will be available during the ablation procedure in the event that surgical intervention becomes necessary.

Biosense Webster, Inc CONFIDENTIAL

### 6.4.3 Precautions

Invasive electrophysiological evaluation and catheter ablation may impart some degree of risk to the subject. The risk of serious complications is generally related to the severity of cardiac disease. The degree of risk of the electrophysiological and catheter ablation procedures versus the potential benefit of the treatment of a paroxysmal or recurrent arrhythmia should be determined by a qualified physician. Cardiac catheterization and electrophysiological procedures should be performed by qualified and appropriately trained personnel in an electrophysiology laboratory. The laboratory should contain sufficient resuscitative equipment and facilities to manage most potential complications. Failure to observe the contraindications, warnings, and precautions in these instructions and the IFU may result in procedural complications. Immediate risks from ablation treatment may include: cardiovascular injury or perforation with or without cardiac tamponade, pulmonary embolus, tricuspid regurgitation, myocardial infarction, bleeding at the catheter insertion site, sepsis, and death.

Contraindications for catheter ablation of arrhythmia include: existing hemodynamic instability, bacteremia, coagulopathy, prosthetic tricuspid valve, intra-atrial or venous thrombosis, and pregnancy.

### 6.5 Known Potential Benefits

Current practice guidelines reflect extensive expert reviews of published risks and benefits among various treatment modalities and patient populations. All key published guidelines agree that the primary clinical benefit of catheter ablation for PAF is an improvement in quality of life, following abatement of arrhythmia-related symptoms.

The role of catheter ablation as first-line therapy, prior to a trial of a Class I or III antiarrhythmic agent, has been suggested as an appropriate indication for catheter ablation of AF in patients with symptomatic paroxysmal or persistent AF by the HRS/EHRA/ECAS 2017 Consensus Statement[4]. In this circumstance, the benefits of catheter ablation outweigh the risks (Class IIa); however, the strength of evidence/data supporting this therapeutic modality (Level B) reflects a limited number of clinical studies. Not all expert bodies are in line with the aforementioned expert opinion.

The 2016 ESC-published guidelines and recommendations for the management of AF suggested that in patients who experience symptomatic recurrences of AF despite antiarrhythmic drug therapy, catheter ablation shows better sinus rhythm maintenance with catheter ablation than on antiarrhythmic drugs[53]. However, the guidelines also present that randomized trials showed only modestly improved rhythm outcome with catheter ablation compared to antiarrhythmic drug therapy[53].

Catheter ablation has been used for over two decades to treat AF patients to achieve PVI. Significant catheter design improvements (e.g., irrigated encircling catheters) focus upon improving physicians' abilities to achieve finite entrance block following PVI, reducing damage to neighboring structures and improving procedural efficiency.

Biosense Webster, Inc CONFIDENTIAL The QDOT MICROTM Catheter is a steerable multi-electrode luminal catheter with a deflectable tip with the force-sensing technology also incorporates six thermocouple temperature sensors and three micro electrodes embedded in the 3.5 mm tip electrode.

The measured temperature allows the operator to assess the efficiency of ablation in real time. Thus providing a highly sensitive measure of catheter location stability and/or movement during RF application and potentially reducing the need for additional RF applications.

The micro electrodes provide high quality localized electrograms that allow finer endocardial electrical mapping and better assessment of possible conduction gaps in the ablation lesion sets used to isolate the pulmonary veins and determining bidirectional block of linear lesion sets.

The catheter tip has incorporated a new angled design of the irrigation ports. This new design allows for reduced incidence/risk of charring and coagulum on the catheter increasing safety during the ablation procedure. With improved contact force information and temperature feedback in any tip tissue orientation, the new QDOT MicroTM catheter is designed to create durable lesions, in shorter time thus reducing the procedural time, and improved irrigation flow with reduction in the amount of fluid load in the patient as compared to a typical irrigation ablation catheter. The catheter also limits conductive heating and collateral damage to neighboring structures including non-cardiac adjacent tissues, improving safety during the procedure[14, 19, 54]

### 7.0 STUDY OBJECTIVES AND PURPOSE

### 7.1 Purpose

The purpose of this study is to demonstrate the safety and 12-Month effectiveness of the QDOT MICROTM catheter when used with the nMARQTM RF generator in the treatment of drug refractory symptomatic paroxysmal atrial fibrillation (PAF) during standard electrophysiology mapping and RF ablation procedures.

### 7.2 Objectives

The primary objective of this clinical investigation is to demonstrate the safety and 12month effectiveness of the QDOT MICROTM catheter when used with the nMARQTM RF generator for pulmonary vein isolation (PVI) in the treatment of subjects with paroxysmal atrial fibrillation (PAF).

- To demonstrate the safety based on the proportion of subjects with early-onset (within 7 days of ablation procedure) primary adverse events
- To demonstrate the 12-month effectiveness based on the proportion of subject with freedom from documented atrial arrhythmia (atrial fibrillation (AF), atrial tachycardia (AT) or atrial flutter (AFL)) episodes during the effectiveness evaluation period (Day 91-365)

The major secondary objectives of this study are:

- To evaluate the incidence of (serious) adverse events during and after procedure up to 3 months following procedure.
- To evaluate Acute Procedural Success as defined by:
  - $\circ~$  The % of subjects with electrical isolation of PVs (entrance block) at the end of the procedure, and
    - The % of subjects with electrical isolation of PVs (entrance block) using QMODE+ as the only ablation strategy
    - The % of subjects with electrical isolation of PVs (entrance block) at all power settings combined
  - The % of subjects with electrical isolation of PVs (entrance block) after first pass isolation, after waiting period and adenosine challenge

### 8.0 STUDY DESIGN AND ENDPOINTS

### 8.1 Description of the Study Design

The QDOT study is a prospective, multicenter, non-randomized clinical evaluation of the QDOT MICROTM catheter in treating subjects with symptomatic PAF who have failed at least one antiarrhythmic drug.

#### Main Study

Up to 185 subjects will be enrolled at up to 30 sites. A Cardiac CT/MRA image subset will be integrated within the Main Study.

### Second (Variable flow) Study

Up to 92 subjects will be enrolled at up to 26 sites.

### **Both Studies**

Effectiveness and safety endpoints have been defined and will be compared to predetermined performance goals. Subjects who sign informed consent are considered enrolled in the study. Enrolled subjects who satisfy all eligibility criteria will then undergo the ablation procedure with the QDOT MICROTM catheter.

After the study ablation procedure, subjects will enter a 3-Month blanking period (Day 0-90).

After the Blanking Period, subjects will enter the Evaluation Period (Days 91-365). Subjects having AF recurrence and/or receiving therapeutic interventions during the evaluation period will be considered effectiveness failures (refer to Section 8.2.2 for all effectiveness failure modes).

All subjects will undergo follow up visits at defined intervals (refer to Table 13.8A Schedule of Treatments and Evaluations). Subjects complete the IDE study after the 12-month follow up visit.

### 8.1.1 Cardiac CT/MRA Subset

### **Main Study**

At a subset of sites, subjects from the Main Study will be enrolled in the cardiac CT/MRA subset and will undergo a 3-month CT/MRA in addition to the baseline CT/MRA (all subjects will have a baseline CT/MRA) to assess incidence of postablation severe PV stenosis. In order to be included in the cardiac CT/MRA population, the subject must have readable outcomes at baseline and 3 months. The first 40 subjects consecutively enrolled in the Main Study (included in the 185 total) at cardiac CT/MRA subset sites who have readable outcomes will be included in the CT/MRA subset (until sufficient CT/MRA subjects are accrued). The probability of observing at least one moderate/severe PV stenosis with 40 subjects is 87% assuming the event rate of moderate/severe PV stenosis is 5%.

In addition to this subset, any subjects with signs or symptoms of PV stenosis will undergo a post ablation CT/MRA. These subjects will not be included in the CT/MRA subset analysis. If severe PV stenosis is present it will be reported as an adverse event.

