### 8.2.3.3 Additional Endpoints

- Procedural Data:
  - Total procedure time, PVI time, RF application time, mapping time and RF application time per lesion
  - Total Fluoroscopy Time and Dose
  - Fluid delivered from the study catheter
  - Location of RF applications, number of RF applications
  - Repeat Ablation Rate
  - RF Ablation parameters per application
  - Device(s) utilized (per ablation)
  - VISITAGTM Settings
  - CF range
  - Power range
  - Tag Index Assessment per anatomical region

**NOTE:** Tag Index data (Force, Power, and Time) will be collected in the CARTO® 3 System during the ablation procedures. The data will be processed to generate the Tag Index.

- Quality of Life:
  - Quality of Life (QOL) status will be evaluated by assessing AFEQT
- Cardiac CT/MRA Subset
  - Incidence of severe PV stenosis at 3 months post ablation in the CT/MRA subset assessment evaluation. The CT/MRA subset will be included in the main study only.

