#### 18.4.3 Other Endpoints

No formal statistical hypothesis and inferential statistics will be formulated and performed for the additional safety and effectiveness endpoints.

Refer to Section 8.2.3.3 for additional endpoints.

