## 18.9.5 Analyses of Secondary and Additional Endpoints

Secondary and additional endpoints will be analyzed separately in each study. Descriptive statistics will be presented for the secondary safety endpoints in the Safety Population.. Descriptive statistics for the secondary effectiveness endpoints will be analyzed in the PP population. For the Main Study, descriptive statistics for additional endpoints will be analyzed in the Safety Population, particularly, incidence of severe PV stenosis will be analyzed in the CMSP population. All of these analyses will be performed after the 12 months follow up is complete. No formal statistical hypotheses and inferential statistics will be formulated and performed for the secondary and additional effectiveness and safety endpoints. Details of analyses methods for secondary and additional endpoints will be provided in SAP.

Biosense Webster, Inc CONFIDENTIAL

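### The CT/MRA subset of 40 is sized on moderate/severe stenosis at 5%, but its endpoint is severe stenosis, where the protocol's own rates give a detection chance of about 18% to at most 33%

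*Protocol*

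**What the plan says.** Protocol 8.1.1 takes "The first 40 subjects consecutively enrolled in the Main Study (included in the 185 total") at the imaging sites, provided that baseline and 3-month images are readable. It gives the purpose as "to assess incidence of postablation severe PV stenosis". The only support for the number 40 is the statement that "The probability of observing at least one moderate/severe PV stenosis with 40 subjects is 87"%, "assuming the event rate of moderate/severe PV stenosis is 5"%. No source or rationale is given for that rate.

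The endpoint in 8.2.3.3 is "Incidence of severe PV stenosis at 3 months post ablation in the CT/MRA subset assessment evaluation". Section 18.9.5 plans that "incidence of severe PV stenosis will be analyzed in the CMSP population". I read this as the set that 18.6 calls CTS. Table 14.2.1A treats moderate (50-70% diameter reduction) and severe (70%) as separate grades.

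On background rates, 6.4.1 states: "Incidence of severe PVS (>70% diameter reduction) was found to be <1% in a recent study with 976 subjects". It then gives 0.5% from a systematic review, without repeating the grade. On inference, 18.4.3 says: "No formal statistical hypothesis and inferential statistics will be formulated and performed for the additional safety and effectiveness endpoints".

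**The concern.** The event used to choose the subset size is broader than the event to be reported. Moderate cases count towards the 87% but not towards the endpoint, and the 5% is well above the rates the protocol quotes for severe stenosis. A reader who wants to know how likely 40 scans are to reveal a severe stenosis finds no answer in 8.1.1, and the one probability printed there belongs to another event.

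What is at stake is how a clean result is interpreted. At the protocol's quoted rates, 0/40 severe stenoses is the most likely outcome. Set beside the 87%, it could look like good evidence that severe stenosis is rare with this device. It would be weak evidence.

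**Working it through.** **Inputs**
- n = 40 subjects with readable images (Protocol 8.1.1). No dropout adjustment is needed, because readability is a condition of entry to the subset.
- p = 5%, moderate or severe (8.1.1).
- p < 1%, severe, above 70% reduction (6.4.1).
- p = 0.5%, grade not restated (6.4.1).
- Cross-check: PV stenosis counts in Appendix C, Table 2, grade not stated: 1/143, 1/157 and 2/164, with blank cells for the other two arms (152 and 161 subjects).

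**Formula.** P(at least one case) = 1 - (1 - p)^40.

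**Plan's own figure.** 1 - 0.95^40 = 0.871. The 87% reproduces.

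**Same formula at the protocol's cited rates**

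| Rate | Source | P(at least one in 40) | P(none in 40) |
|---|---|---|---|
| 1% (upper limit of the cited rate) | 6.4.1 | 1 - 0.99^40 = 33.1% | 66.9% |
| 0.5% | 6.4.1 | 1 - 0.995^40 = 18.2% | 81.8% |
| 4/777 = 0.51% (blanks counted as zero) | Appendix C | 18.7% | 81.3% |
| 2/164 = 1.2% (highest arm) | Appendix C | 38.8% | 61.2% |

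Even the highest of these is less than half of 87%.

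**What 87% would need.** n = ln(0.13)/ln(1 - p), rounded up: 204 subjects at 1% and 408 at 0.5%. With n = 40, the rate must be 1 - 0.13^(1/40) = 4.97%.

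**What 0/40 would show.** The exact two-sided 95% upper limit is 1 - 0.025^(1/40) = 8.8%. This is about nine times a rate of 1%, and it does not exclude 5% either.

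**The case against.** **The 87% is properly labelled.** The sentence names both its event and its rate, and says nothing about severe stenosis alone. This stands: there is no arithmetic error and no false statement. The gap is that no figure is given for the endpoint itself.

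**No decision depends on it.** The endpoint is an additional, descriptive one with no hypothesis or threshold. This also stands. A reader might infer that the trial is underpowered, or that the 185-subject sample size is affected. The documents support neither.

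**Surveillance does not rest on these 40 alone.** Any subject with signs or symptoms of stenosis is imaged outside the subset (8.1.1, 13.7). PV stenosis is also a primary adverse event up to 90 days (8.2.1), counted above 70% narrowing with or without symptoms and from 50% with relevant symptoms (Table 14.2.1A). So one should not conclude that severe stenosis would go undetected across the trial. Planned routine 3-month imaging of subjects without symptoms is, however, confined to the subset.

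**The interval is largely planned.** Sections 18.5 and 18.9.1 make exact two-sided 95% intervals the general convention. This mostly stands, although 18.4.3 and 18.9.5 rule out inferential statistics for additional endpoints and so leave its use here unclear.

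**The 18-33% is soft.** The 1% is an upper limit, the 0.5% may cover all grades, and both are literature rates rather than rates for this ablation mode. The 5% could have been meant as a rate of concern rather than a background rate. All fair; but the protocol does not say which, and no reading makes the 87% a figure for severe stenosis.

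**Moderate cases may be tabulated anyway.** The SAP supplied covers only the Variable Flow study, while the subset belongs to the Main study, whose SAP is a separate document. It therefore cannot be claimed that moderate stenosis will go unreported.

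**Conclusion.** The concern holds as a mismatch between the event that sizes the subset and the event it is meant to estimate. For severe stenosis, 40 subjects give a detection chance of at most about 33% from the cited rate below 1%, and about 18% at 0.5%, against the 87% printed for a broader event. If the 0.5% covers all grades, the figure for severe stenosis at that source is below 18%. These values assume independent subjects and that the literature rates carry over to this device; they are approximate.

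A reader might go further and conclude that the endpoint should be replaced by moderate-or-severe stenosis so that the 87% fits. The documents do not support this. Severe stenosis is the prespecified endpoint in three sections, and changing it to suit a sample-size sentence would dilute the more serious outcome. The primary endpoints and study success are untouched.

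**What to change.** 1. Keep severe stenosis as the subset endpoint.
2. In 8.1.1, state that the 87% applies only to moderate/severe stenosis at 5%, and give the source or rationale for the 5%, including whether it is an expected rate or a rate of concern.
3. Add that the chance of seeing at least one severe stenosis in 40 subjects is roughly 18-33% at the rates in 6.4.1, with 33% as a ceiling for the source quoted as below 1%.
4. Tabulate reductions of 50% or more as an additional row, from the same images reviewed by the core lab (13.12). Label the row as added if subset results have already been seen.
5. Show the exact 95% interval for both rows, and say that the convention in 18.5 and 18.9.1 applies here.

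The cost is a few sentences, one table row and two intervals. No extra subjects or scans are needed. Section 13.2 spells out the core lab's diameter measurements only for baseline, but grading a stenosis as severe already requires a baseline and a 3-month diameter, so the added row should need no new readings.
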